7. Participants will then complete follow-up psychosocial and health economics questionnaires two weeks after being notified of their CT results, or notification that they are on the control arm of the trial.

Figure 1: UKLS Trial Design

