14.3 Psychosocial and Health Economics

A subset of participants will be asked to take part in the Psychosocial evaluation and Health Economics section of the study. Equal numbers from each study arm will be asked to take part. These participants will be selected at random from the original 4,200 randomised. A brief baseline psychosocial questionnaire will be completed at the clinic recruitment session. Follow-up psychosocial questionnaires will be sent directly to all participants at 1 month post randomisation (i.e. in the screening group, approx. 2 weeks after CT scan results are received – both baseline and follow up scans). These data will be scanned and uploaded onto the UKLS database and analysed.

One objective of the psychosocial evaluation is to assess potential participation bias to the UKLS pilot trial and highlight potential hard to reach groups within this cohort. Analyses will compare the following groups on age, gender and socio-economic status: 1) non-responders, 2) those who complete the non-participation questionnaire (negative responders) and 3) those who complete the UKLS 1st questionnaire (positive responders).

In order to complete these analyses the mail sorting organisation working with UKLS (RADAR) will provide the UKLS study team with data on age and gender of non-responders to the initial approach letter. RADAR will compute the Index of Multiple Deprivation (IMD) scores (a measure of socio-economic deprivation) for all approached individuals using their postcodes and release the IMD information to the UKLS team. The data sent to UKLS is non-identifiable (age, gender and IMD score of each individual).

We have contacted the National Information Governance Board for Health and Social Care (NIGB) who have informed us that we do not need to submit an amendment to them because the proposed analyses are compatible with the purpose of the original NIGB application and there is no flow of patient identifiable information as the UKLS team receive anonymised data from RADAR. Evidence of this can be found within the UKLS Trial Master File.

The Health Economics questionnaire data will be analysed at Nottingham University under the direction of Professor [name].

Psychosocial analysis plan

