We now require estimates of the various quantities. Let us first suppose that we shall be selecting a fairly high risk group for the trial, with a minimum annual incidence of five per thousand and an average annual incidence of seven per thousand. Thus $I=0.007$. From a recently published overview, we have estimates $\lambda_1=0.49$ and $S=0.96$ [28]. Five-year survival from lung cancer in the UK has been reported as 6% [29], corresponding to $\lambda_3=0.56$. Henschke et al [30] report 85% 10-year survival of 412 stage I screen-detected cases. Assuming that the 72 screen-detected cases in their series with stage II or worse disease had zero ten-year survival, this would give an overall ten-year survival of 72%. Hypothesising further that this is artificially high as a result of length bias/overdiagnosis, we assume a ten-year survival of 50%. Thus we are estimating the effect of screening on mortality from the 'real', life-threatening tumours, rather than inflating the incidence of the intervention group and retaining the very high survival rate. This gives $\lambda_2=0.07$. We assume an uptake rate of 80%, which seems high but reflects the motivated nature of this group, already demonstrated by their positive response at two stages of approach.

WALD Single Screen Design

The resulting estimates of cumulative lung cancer mortality are shown in Table 1, adjusted for the 80% compliance. The Table also shows the relative risks of lung cancer death, and the numbers required per group (assuming equal group size) for 90% power to detect the difference as significant, with 2-sided testing at 5% level. The optimum time of analysis would be at the end of three years, and 16,000 subjects per group would be required (32,000 in all). The time to the result, taking into account the recruitment period, would be more likely to be around five years.

Year	Cumulative lung cancer mortality (study)	Cumulative lung cancer mortality (control)	RR (intervention vs control)	Number required per group
1	1.0	1.2	0.83	368,000
2	3.1	4.0	0.78	63,000
3	5.3	7.8	0.69	16,000
4	9.2	12.1	0.76	20,000
5	13.4	16.7	0.80	21,000
6	17.9	21.4	0.83	24,000

Annual screening for three years

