17.4.2 Questionnaires

The majority of the data collected for the trial will be obtained directly from the participant using lifestyle and psychosocial and Health Economics questionnaires. These questionnaires will form the basis for participant selection. Follow-up questionnaires will also be sent out during the course of the trial to collect further psychosocial data. For the non-screen arm participants will receive a psychosocial questionnaire two weeks after randomisation to the non-screen arm. In the screen arm participants will receive a psychosocial questionnaire two weeks after receiving the result of their baseline scan and any follow up scans required. Data will also be collected during clinic visits. This data will be recorded within patient notes (Source Data) and will be entered onto the UKLS database where necessary.

Timetable of psychosocial measures	Baseline	Follow-up
Demographic and clinical information 
 • Ethnicity • Socioeconomic status / education • Lung screening history (past lung screening; past recall) • Gender* • Age (DOB)* • Smoking – type and frequency* • Family history of lung cancer* 
* Could be accessed from 1st screening risk questionnaire
	✓ ✓ ✓ ✓ ✓ ✓ ✓	x x x x x x x
Cancer distress 6 item Cancer Worry Scale (CWS-R) adapted to lung cancer	✓	✓
General distress Hospital Anxiety and Depression Scale (HADS)	✓	✓
Satisfaction with Decision Scale SWD Scale [34] adapted to decision to take part in lung screening study	✓	✓
Screening expectations & perceptions of CT scan results CARA model [24] Feedback expectancy, i.e. expected CT scan result. To be completed by intervention arm only: perceived feedback threat (“How concerned were you by your CT scan result?” where 1 = not at all concerned, 5 = extremely concerned) and perceived feedback accuracy (“How likely did you think it was that your CT scan result was false or inaccurate?” where 1 = not at all, 5 = a great deal)	✓ x	x ✓
Screening behaviours 
 • Intention to attend further screening • Use of private CT scans 	x x	✓ ✓

Following a Quality Control check and audit of UKLS data captured electronically from the UKLS questionnaires; original copies of the questionnaire will be securely destroyed. Images of every questionnaire will be stored on the UKLS database and affiliated with the relevant participant.

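### CT-arm participants who are never scanned have no stated route to the follow-up questionnaires, so the psychosocial comparison risks becoming scan attenders against all surveyed controls

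*Protocol*

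**What the plan says.** Three places in the protocol set the timing of the follow-up questionnaires.

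- **Section 17.4.2 (psychosocial).** For those allocated to CT: "In the screen arm participants will receive a psychosocial questionnaire two weeks after receiving the result of their baseline scan and any follow up scans". For controls: "For the non-screen arm participants will receive a psychosocial questionnaire two weeks after randomisation to the non-screen arm".
- **Section 6.3, item 7 (psychosocial and health economics).** The forms are completed "two weeks after being notified of their CT results, or notification that they are on the control arm of the trial".
- **Section 14.3 (psychosocial).** "Follow-up psychosocial questionnaires will be sent directly to all participants at 1 month post randomisation". The bracket that follows explains this for the screening group as about two weeks after CT results are received.

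Section 14.3 also says that the evaluation is done in a randomly chosen subset of unstated size: "Equal numbers from each study arm will be asked to take part". Its analysis plan tests the main effect of trial condition on cancer worry (the primary psychosocial outcome), anxiety, depression and decision satisfaction. It uses repeated measures analysis of covariance from baseline to four weeks, controlling for variables such as baseline distress. A preliminary analysis describes who does not return questionnaires.

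Under Section 8.3 the CT appointment is sent with the allocation letter, so attendance is decided after randomisation. Section 15.2 sets expected attendance: "We assume an uptake rate of 80" per cent. Section 7.3 says that follow-up generally continues after withdrawal from the intervention unless the participant also withdraws consent to follow-up.

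**The concern.** The control form depends only on allocation. The CT-arm form, as worded in Sections 6.3 and 17.4.2, depends on something that happens after allocation and is partly the participant's choice: attending the scan and receiving a result. Anyone allocated to CT who declines or misses the appointment never reaches the trigger.

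If the mailing follows that wording, a self-selected part of one arm is missing at follow-up while the matching people among the controls are retained. The planned test of trial condition is then no longer a comparison of the randomised groups. Not attending is plausibly related to worry about cancer and to satisfaction with the decision to take part, which are outcomes of this analysis. Baseline adjustment can remove the part of the difference that was already measured at baseline, but not a part that develops after allocation. The attrition analysis can describe the loss. It cannot recover answers from people who were never sent a form, and nor can a later statistical analysis plan.

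**Working it through.** **The triggers side by side**

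| Section | Questionnaires | CT arm starts from | Control arm starts from |
|---|---|---|---|
| 6.3 item 7 | psychosocial and health economics | CT result | notification of allocation |
| 14.3 | psychosocial | one month after randomisation, explained as about two weeks after CT results | one month after randomisation |
| 17.4.2 | psychosocial | CT result | randomisation |

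No row gives a date for a CT-arm participant without a result. Section 14.3 would do so if its opening words stood alone, but its own bracket returns to the result.

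**Inputs**

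- Uptake u = 0.80 (Section 15.2).
- CT arm: 2,100 in the pilot and 16,000 in the main trial (Section 6.3, item 6).
- Pilot controls: 2,100, taken from the 4,200 randomised in Section 14.3 and the 1:1 ratio in Section 8.3. (Section 6.3 item 6 gives a pilot total of 4,000; the CT-arm figure is 2,100 either way.)
- d, the attender minus non-attender difference in follow-up score in SD units, after baseline adjustment: not in the documents. Assumed 0.2 to 0.3.

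**Step 1: the protocol's own figure.** Section 15.2 expects 12,800 scans in the single-screen trial: 0.80 x 16,000 = 12,800. It reproduces.

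**Step 2: how many have no trigger.** (1 - u) x arm size.

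- Pilot: 0.20 x 2,100 = 420. This is a maximum that applies if the whole arm is surveyed; in a random subset it is 20% of those invited.
- Main trial, if all were surveyed: 0.20 x 16,000 = 3,200.
- Pilot at other uptakes: 210 at 90%, 525 at 75%, 1,050 at 50%. Section 15.4 would still go ahead, after revision, at 50 to 74% compliance.

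**Step 3: bias.** The full CT-arm mean is u x m(attend) + (1 - u) x m(not attend). Measuring attenders only gives m(attend). The difference is (1 - u) x [m(attend) - m(not attend)] = (1 - u) x d.

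- u = 0.80: d = 0.2 gives 0.04 SD; d = 0.3 gives 0.06 SD.
- u = 0.50: d = 0.2 gives 0.10 SD; d = 0.3 gives 0.15 SD.

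This does not depend on the number surveyed.

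**Step 4: effect on the test, for illustration.** With no true effect of allocation and a two-sided 5% normal test, SE = sqrt(1/n1 + 1/n0) and the rejection rate is Phi(bias/SE - 1.96) + Phi(-bias/SE - 1.96).

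| Surveyed per arm (analysed, CT v control) | SE (SD) | d = 0.2 | d = 0.3 |
|---|---|---|---|
| 2,100, whole pilot (1,680 v 2,100) | 0.033 | 23% | 45% |
| 500, assumed subset (400 v 500) | 0.067 | 9% | 15% |

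For the whole pilot the ratios bias/SE are 0.04/0.0327 = 1.22 and 0.06/0.0327 = 1.83. All four rates assume full response and take no account of any precision gained by adjustment. If d is read as a raw difference, they also ignore the part that baseline adjustment would remove.

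**The case against.** A reader might infer that the protocol excludes non-attenders from questionnaire follow-up by design. The documents do not support that. Section 14.3 names all participants and a date counted from randomisation, and its bracket can be read as showing where that date falls for someone who was scanned. The four-week endpoint fits that clock, and Section 7.3 favours continued follow-up. This stands: the text is inconsistent and leaves a gap; it does not state an exclusion. It does not remove the point, because two of the three sections give only the result-based trigger and the third explains itself by it.

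A reader might also take 23% and 45% as the false-positive rate of the planned analysis. They are not. They assume the whole pilot surveyed, full response, no baseline adjustment and a value of d with no source. Section 14.3 plans a subset and an adjusted analysis. If allocation truly has no effect, attenders and non-attenders differ only in their own characteristics or course, and baseline adjustment removes part of that. These rates are an upper illustration. A bias of 0.04 to 0.06 SD is also small in itself.

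A third inference would be that the cost-effectiveness objective is equally compromised. Only Section 6.3 item 7 ties the health economics forms to the CT result. Cost effectiveness is listed for the main trial, whereas the 420 is a pilot figure. How far these forms feed that objective is not spelled out.

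Finally, analysis by allocated arm and the handling of missing forms may properly be left to the analysis plan. That is fair for the analysis, but not for the decision whom to send a form.

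**Conclusion.** The point holds in limited form. Sections 6.3, 14.3 and 17.4.2 disagree on when the follow-up questionnaire is sent, and none gives a date for a CT-arm participant who is never scanned. Applied as worded in Sections 6.3 and 17.4.2, about 20% of the surveyed CT arm would drop out of the comparison at the protocol's own uptake, with no matching loss among surveyed controls. The resulting bias is (1 - uptake) x d: 0.04 to 0.06 SD under the assumed d of 0.2 to 0.3, and more if uptake is lower. Its effect on the test cannot be fixed from the documents, because neither d nor the subset size is given.

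The scope is the questionnaire outcomes: the psychosocial ones and, by Section 6.3 only, the health economics ones. Cancer and death follow-up of all randomised participants runs through the registries (Sections 14.1 and 14.2), so the mortality comparison is not affected. This is a cheap improvement that also resolves a contradiction.

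**What to change.** Reconcile Section 6.3 item 7, Section 14.3 and Section 17.4.2 so that they state one rule:

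- The first follow-up questionnaire goes to every surveyed CT-arm participant, scanned or not.
- A participant with no scan result by the usual CT-arm send date gets the form at a default date counted from notification of allocation.
- Only the items about the CT result are left out for those not scanned.
- The arms are compared as randomised.
- State whether the same rule covers the health economics questionnaire.

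The cost is protocol wording, one default date in the mailing system and at most about 420 extra postal forms in the pilot, fewer with a subset. Response among non-attenders will probably be lower, so some imbalance may remain. It would then be visible as non-response and open to analysis, because the forms would have been sent.

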17.4.3 UKLS Database

Discussions have taken place between the UKLS CI and the Steering Committee of the NELSON trial and it has been agreed that the UKLS trial may have use of their database and adapt as required for a fee during the pilot and main trial.

The IT manager for NELSON, [name] [name], has been appointed as the UKLS IT Database Consultant.

The UKLS database will be housed by the University of Liverpool Computer Services Department. The database will be housed on its own server. Access to areas of the database will be allocated on a need to know basis as authorised by the CI.

18 Trial Monitoring

18.1 Trial Monitoring

Central and site monitoring is conducted to ensure the rights and well-being of participants are protected during the course of a study, and that trial procedures, laboratory and data collection processes are of high quality and meet sponsor requirements. A risk assessment for the study will be carried out prior to the start of patient registration, to determine the level and type of monitoring required and subsequent monitoring plan will be developed to document the central (and potentially site) monitoring, at what frequency monitoring will be carried out, and the level of detail at which monitoring will be conducted.

18.2 Risk Assessment

In accordance with the LCTU Standard Operating Procedures and the requirements of the sponsor organisation a study risk assessment will be completed in partnership with the Trial Management Group.

In conducting risk assessments, the contributors consider potential patient, organisational and study hazards, the likelihood of their occurrence and resulting impact should they occur.

18.3 Source Data

Source data is all information in original records and certified copies of original records of clinical findings, observations, or other activities in a clinical trial necessary for the reconstruction and evaluation of the trial. Source data are contained in source documents (original records or certified copies; ICH E6, 1.51).

18.4 Monitoring at LCTU

18.4.1 The Green Light Process

The green light process in place at the LCTU means that no patients can be registered at a particular site without the green light being given. It ensures that all approvals must be in place, all contracts/agreements signed and all study-specific and GCP training received by the site research staff before patients can enter the study. The green light will be granted by the trial co-ordinator (TC), once all essential documents are in place.

18.4.2 Site Research Staff

All site research staff involved in the study must be included in the delegation log. The PI at each site signs off on the delegation log only those staff members he/she feels are able and competent to complete the assigned tasks. The delegation log provides clearly defined delegation of responsibility thus ensuring site research staff are aware of their responsibilities.

The TC ensures that all delegated staff have documented study-specific training (on the protocol, SAE reporting and consent process) all of which is provided at site initiation (either on site or by teleconference) by the TC and on a continuous basis throughout the study when new staff are added to the delegation log. Sites are supplied with copies of training aids presented at site initiation to provide a constant

reminder of key study issues. Delegated study research staff must also submit their CV and provide the date of their last ICH GCP training. In order to ensure that site research staff maintain up to date ICH GCP training (to be renewed every 2 years as suggested by ICH GCP), an automated email reminder is sent to site research staff when their next ICH GCP training is due. Non-NHS staff must have honorary contracts and evidence of CRB checks must be obtained for staff (when necessary by UK law).

Automated 6-monthly email reminders (from site opening) are sent to sites requesting that an updated delegation log is faxed to the LCTU. On receipt of updated delegation logs, the TC ensures that new staff have submitted their CVs and date of last ICH GCP training, as well as providing them with trial-specific training.

18.4.3 Randomisation

The TC verifies that all site research staff have attended study specific training related to eligibility screening and the informed consent process. Prior to randomisation, the TC/data manager (DM) carry out a check of all consent forms sent to the LCTU. This includes checking that the patient is eligible, the correct versions of the PIS and ICF have been used, and the patient and clinician signatures are present and dated on the same day. LCTU staff receive appropriate randomisation training and there is always office cover to ensure the randomisation procedure is carried out correctly.

18.4.4 Patient Confidentiality

Participant identifiable information is required throughout the trial to contact participants, assess scan, monitor the trial and to collect Office of National Statistics Data. Patient confidentiality is very important and the participant identifiable information will be stored on a database hosted on the secure University server. The steps below have been put in place to ensure data security:

- All desktop computers and servers will require user name and password to gain access
- All computers will only be used either standalone or behind a hardware and software based firewall
- Any internal/external access to the system will only be provided to essential staff
- External access will require user name and password to be provided
- All passwords will be amended on a quarterly basis
- All password complexity is enforced by University Policy
- McAfee antivirus
- Software will operate on all desktop computers, laptop computers and servers
- Any sensitive data sent by, CD, DVD or external Hard Drive will be contained within an encrypted zip file and password protected.
- All retired hardware will have their disk drives either scrambled or physically destroyed.

The UKLS team will have access to this data on a need to know basis and this will be decided by the Chief Investigator. The laboratory and statistical teams will not recover identifiable information of any kind and will recognise participants by a seven digit code number.

Participant names and addresses will be stored by the LCTU for the purpose of approaching participants to take part in the study and for sending subsequent questionnaires during the course of the study. Participant Information Sheets will reflect that this data will be collected and stored. Data for participants that do not give informed consent will be encrypted and only the database developer will have access to this information. For the purposes of the LCTU participants will only be identified by trial number and/or initials only.

Individual participant medical information obtained as a result of this study is considered confidential and disclosure to third parties is prohibited.

Consent forms sent to the LCTU as part of the randomisation process may contain patient identifiers for the purpose of monitoring as described in the study risk assessment. Such information will be stored in secure, locked cabinets

18.4.5 Recruitment

The TC will provide monthly recruitment reports, to allow the IDSMC, TSC and TMG to regularly review recruitment across sites. Slow or inconsistent recruitment will trigger further action centrally. The TC may liaise directly with site staff in order to query reasons for slow recruitment and try to resolve any problems that could impact recruitment. TC will check that the trial is being actively promoted at sites and site recruitment schedules will be reviewed during the course of the trial as necessary.

